ranked secondary analyses; the PHQ-9 provides a brief screening complement and the MADRS a clinician-rated perspective sensitive to change. Similarly, the NIH-BFI offers a multi-dimensional clinician-rated fatigue assessment, while the FSS captures subjective functional impairment. Instruments measuring religiosity (DUREL), quality of life (SF-12), hypomanic symptoms (HCL-32), sleep (PROMIS), meaning in life (PIL), and subjective well-being (SHS) are included for descriptive and exploratory purposes and are not part of the ranked secondary outcome hierarchy. Assessment burden was considered during protocol development; instruments are administered in a fixed, piloted order, and estimated completion time per assessment visit does not exceed 60 minutes.

Sample size and power

We power the primary analysis (time-to-first attempt) using Schoenfeld's method for Cox models [32]. Assuming a hazard ratio (HR) = 0.50 (BCBT vs ST), two-sided $\alpha=0.05$, and 80% power, the number of required events is:

$$E=[\ln(HR)]^2(Z_{1-\alpha/2}+Z_{1-\beta})^2$$

If the overall 6-month event rate is ~15% in this high-risk sample (e.g., 20% ST vs 10% BCBT), then $N \approx 113$ would be required to accrue ~17 events. To accommodate 25% attrition, we plan $N=150$ (75 per group), yielding $\geq 80\%$ power under these assumptions. This sample also provides $\geq 80\%$ power to detect small-to-moderate between-group effects (e.g., standardized mean difference $d \approx 0.38$) on continuous secondary outcomes with repeated measures.

Statistical analysis plan

- Principles: Intention-to-treat primary; $\alpha=0.05$, two-sided; 95% CIs. Time zero is defined as the date of randomization. Follow-up begins at randomization and continues until first suicide attempt, death, withdrawal of consent, or administrative censoring at the 6-month assessment, whichever occurs first. Any suicide attempt occurring after eligibility screening but before

randomization will be documented as a baseline clinical event but will not count as a primary outcome event; this ensures that the risk period is aligned comparably across both arms from the moment of allocation.

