- Primary analysis: Cox model estimating HR for BCBT vs ST, adjusting for stratification factors (sex, prior suicide attempt), with additional covariates (age and baseline suicidal ideation) included in sensitivity analyses. Check proportional hazards (Schoenfeld residuals); if violated, use time-varying effects or restricted mean survival time. Given approximately 17 anticipated events, including four covariates yields an events-per-variable (EPV) ratio of ~4, below the commonly recommended threshold of 10. To reduce the risk of overfitting, the pre-specified primary model will include only the two stratification factors (sex and prior suicide attempt) as covariates (EPV ~8.5). Adjustment for age and baseline suicidal ideation will be conducted as a supplementary sensitivity analysis.
- Secondary analyses: Linear mixed-effects models (random intercepts) for fixed effects: time, group, group×time; GEE/logistic models for binary outcomes (e.g., any NSSI).
- Missing data: Missing At Random (MAR) is defined as missingness that depends only on observed data; Missing Not At Random (MNAR) refers to missingness that depends on unobserved data (e.g., patients drop out because their suicidal ideation worsened). Time-to-event outcome: participants lost to follow-up will be censored at the date of last confirmed contact. Sensitivity analyses will include: (a) best-case scenario—all BCBT dropouts are assumed attempt-free (censored at day 180) while all ST dropouts are assumed to have attempted at their last contact date; (b)

worst-case scenario—the reverse; (c) tipping-point analysis—identifying the minimum assumed increase in hazard for censored BCBT participants that renders the primary result non-significant.

- Exploratory moderators (hypothesis-generating only): These analyses are explicitly exploratory. Given the projected sample size and anticipated number of primary events, treatment-by-baseline interaction tests are underpowered for definitive subgroup inference and must not be interpreted as confirmatory evidence of effect heterogeneity. Interactions of treatment with baseline factors (e.g., prior attempt, sex, age, baseline symptom severity) will be examined with marginal effects and graphical probes. Mediation (e.g., change in cognitive distortions) may be explored descriptively if data allow. All findings will be framed as generating hypotheses for future adequately powered trials.

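### The claim of at least 80% power at d ≈ 0.38 for continuous secondary outcomes is not secured by the stated mixed model at moderate correlation on five visits with 25% attrition

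*Protocol*

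**What the plan says.** Under Sample size and power, N is set by the primary outcome: about 113 participants for about 17 events, and then, "To accommodate 25% attrition", 150 participants (75 per group). The same paragraph adds that this sample gives at least 80% "power to detect small-to-moderate between-group effects", with a standardized mean difference of about 0.38 as the example, "on continuous secondary outcomes with repeated measures". It does not say which visits, contrast, within-person correlation or retained sample size lie behind that figure.

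The Secondary analyses bullet of the Statistical analysis plan section gives the model: "Linear mixed-effects models (random intercepts) for fixed effects: time, group, group×time". It names no baseline covariate, does not say whether time is linear or categorical, and does not say which term or contrast is the treatment test. The Principles bullet sets two-sided alpha at 0.05. The Multiplicity bullet plans no adjustment for secondary outcomes and calls them exploratory.

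The Abstract lists five assessments: baseline, weeks 6 and 12, and the 3- and 6-month follow-ups. Table 2 of the Supplementary Material marks BSI, BDI-II and GAD-7 at all 16 columns, T0 to T15.

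**The concern.** A printed power figure should follow from the printed design. A plain two-group comparison at d = 0.38 needs 109 per arm and the trial has 75, so the claim rests wholly on what the repeated measures add. That gain depends on the contrast and the correlation, and the model as written does not take the most dependable gain available, adjustment for the baseline score.

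The stake is how null secondary results will be read. Suicidal ideation heads the secondary hierarchy, and Hypothesis 2 predicts similar improvement in anxiety and depression in the two arms. If the real sensitivity is below the stated one, the absence of a difference will look more informative than it is.

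**Working it through.** **Inputs from the Protocol.** d = 0.38; two-sided alpha 0.05; 80% power; 75 per arm; 25% attrition, which leaves 0.75 × 75 ≈ 56 per arm; five assessments (Abstract) or 16 columns (Table 2).

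**Assumptions, not in the Protocol.** Equal correlation rho between any two visits (compound symmetry, which a random-intercept model implies), equal variance at each visit, and a normal approximation. The central value is rho = 0.5, with the range shown below.

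**Formula.** Detectable d = 2.802 × √(2V/n), where V is the variance of the contrast in units of the single-visit variance and n is the number per arm.

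**Can the stated figure be reproduced?** Not uniquely. Solving for V at d = 0.38 and 80% power gives V = n × 0.1444 / (2 × 2.802²), which is 0.690 at 75 per arm and 0.515 at 56 per arm. A single visit with no repeated measures has V = 1, so power is 64% / 52%. V = 0.690 at 75 per arm is met, for example, by one baseline-adjusted visit at rho ≈ 0.56 (1 − 0.56² ≈ 0.69) or by the plain average of four visits at rho ≈ 0.59 ((1 + 3 × 0.59)/4 ≈ 0.69). Both require that nobody is lost.

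**Power at d = 0.38 and rho = 0.5**

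| Contrast | V | V at 0.5 | 75 per arm | 56 per arm |
|---|---|---|---|---|
| Group×time, one visit against baseline | 2(1 − rho) | 1.00 | 64% | 52% |
| Linear group×time slope, five visits | (1 − rho)/Sxx | 0.90 to 0.78 | 69–75% | 56–63% |
| Average of four follow-up visits | (1 + 3rho)/4 | 0.625 | 84% | 72% |
| That average minus baseline | (1 + 3rho)/4 + 1 − 2rho | 0.625 | 84% | 72% |
| One visit, baseline-adjusted | 1 − rho² | 0.75 | 77% | 64% |
| Average of four, baseline-adjusted | (1 + 3rho)/4 − rho² | 0.375 | 97% | 91% |

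For the slope, time is scaled from 0 to 1 and d is the difference at the last visit. Sxx is 0.555 for weeks 0, 6, 12, 13, 26 (follow-ups counted from randomization) and 0.644 for weeks 0, 6, 12, 24, 36 (counted from the end of treatment).

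**Correlation needed for 80%**

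| Contrast | 75 per arm | 56 per arm |
|---|---|---|
| One-visit group×time | at least 0.66 | at least 0.74 |
| Five-visit slope | at least 0.56–0.62 | at least 0.67–0.71 |
| Average of four, unadjusted | at most 0.59 | at most 0.35 |
| Average of four minus baseline | at least 0.45 | at least 0.59 |

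The unadjusted average needs a low correlation and the change contrasts need a high one. A power figure therefore means little unless contrast and correlation are stated together.

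**Gradual dropout.** The 56-per-arm column treats dropouts as contributing nothing, so it is a lower bound. With monotone dropout reaching 25% and all observed data used, the one-visit contrast has about 56–57% power at rho 0.5, 77–79% at 0.7 and 84–85% at 0.75. The five-visit slope has about 60–66% at rho 0.5.

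**Table 2 schedule.** A linear slope over 16 visits at rho 0.5 gives 98% / 94% if visits are equally spaced, and about 93% / 84% with an assumed calendar spacing to week 26. These figures assume that individual slopes do not vary, as the random-intercept model does; they are optimistic if slopes do vary.

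**The case against.** The strongest reply is that no arithmetic error has been shown. The power sentence speaks of a between-group mean difference with repeated measures. It does not commit to group×time as the powered test, and the model bullet lists group as well. A one-visit change score at rho 0.5 gains nothing over a single visit, so it is the least generous reading. On Table 2's 16 columns a group×time slope in the stated model passes 80% at rho 0.5 even with 56 per arm. Correlation and time coding for secondary outcomes are often left to a statistical analysis plan. N does not depend on this sentence, and the planned 95% confidence intervals will show what a null result excludes.

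Most of this stands, and it rules out two stronger readings. A reader might infer that the claim is simply false for the stated model. The documents do not show that, because they fix neither the contrast nor the correlation, and they carry two schedules. A reader might also infer that the claim needs almost no attrition. It does not: at rho 0.75 even the one-visit contrast has 81% power with 56 per arm.

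What the reply does not remove is that the Protocol itself prints both the figure and the model. Its secondary objective is to compare trajectories, which makes group×time a natural reading. On the Abstract's schedule, none of the four unadjusted contrasts above reaches 80% at rho 0.5 with 56 per arm. The 16-column rescue relies on a schedule that conflicts with the Abstract.

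**Conclusion.** The power statement is unsupported and depends on unstated assumptions; it is neither confirmed nor refuted. Under compound symmetry with rho = 0.5, five visits and the paragraph's own 25% attrition, power at d = 0.38 lies between 52% and 72% for the unadjusted contrasts that the stated model offers. Without attrition it lies between 64% and 84%. The claim holds at rho of about 0.74 or more for the one-visit contrast with 25% attrition, or for a linear slope over the Table 2 schedule at moderate correlation.

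The substantive weakness is the analysis, not only the missing detail. Leaving out the baseline score gives up precision that the data already collected at T0 would provide. At rho 0.5, adjustment lifts one-visit power from 64% to 77% (75 per arm) or from 52% to 64% (56 per arm). The consequence is limited, since the primary outcome is the sole confirmatory endpoint.

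**What to change.** 1. In the Secondary analyses bullet, for continuous secondary outcomes measured at T0 (as Table 2 is printed, BSI, BDI-II and GAD-7 among the ranked scales), include the baseline score as a covariate, or constrain the baseline means to be equal across arms. C-SSRS is not marked at T0 there, so its ideation score needs its own statement.
2. In the same bullet, name the treatment contrast. The difference averaged over the four post-baseline visits detects d of about 0.28 (75 per arm) to 0.33 (56 per arm) for rho from 0.3 to 0.5. At rho 0.5, for example, 2.802 × √(0.75/75) = 0.28 and 2.802 × √(0.75/56) = 0.32. This is a different question from the difference at 6 months. If 6 months is what matters, the baseline-adjusted one-visit contrast at rho 0.5 detects about 0.40 to 0.46.
3. In Sample size and power, restate the figure for that contrast with its assumed correlation, number of visits and attrition.
4. Reconcile the five assessments of the Abstract with the 16 columns of Table 2.

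Items 1 to 3 cost about one sentence in each of the two sections and need no new data for scales already taken at T0. Item 4 is a decision on the schedule that should be settled in any case. If the model is kept as it is, the restated figure will be less favourable: for the one-visit contrast at rho 0.5, d of about 0.46 (75 per arm) to 0.53 (56 per arm).

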Secondary objectives: Compare trajectories of suicidal ideation, NSSI, depression, and anxiety; evaluate feasibility/acceptability; explore predictors and moderators of response (e.g., prior attempts, sex, age, symptom severity).

Hypotheses

1. BCBT will yield a lower hazard of suicide attempt (superiority).

2. BCBT and ST will show similar improvements in general anxiety/depression, but BCBT will outperform ST on suicide-related outcomes.
3. BCBT will demonstrate high feasibility and acceptability in this population, as reflected by satisfactory recruitment rates, session attendance, treatment adherence, and positive patient satisfaction ratings.
4. Baseline characteristics, including history of prior suicide attempts, baseline symptom severity, age, and sex, will be associated with differential clinical outcomes over follow-up.

Methods

Trial Design

Single-site, parallel-group, superiority RCT (1:1) with blinded outcome assessment and 6-month follow-up. The protocol follows the SPIRIT 2025 guidelines; reporting will follow the CONSORT 2025 guidelines and the extensions for non-pharmacological interventions and harms.

Randomization

Participants will be randomly assigned in a 1:1 ratio, stratified by sex and prior suicide attempt, using a computer-generated permuted-block randomization sequence with variable block sizes (blocks of 4 and 6) to prevent allocation prediction. The sequence will be generated by an independent researcher with no involvement in participant recruitment or outcome assessment, using validated statistical software. Participants will be enrolled by the study coordinator; treatment allocation will be released only after eligibility is formally confirmed and informed consent is obtained. Allocation concealment will be maintained through a centralized, web-based randomization module within REDCap, which withholds the assigned arm until the enrollment step is completed and locked. Neither the enrolling clinician nor the participant will have access to forthcoming allocations.

Blinding

Given the nature of psychotherapy research, blinding of participants and therapists to treatment allocation is not feasible (Cuijpers et al., 2015). However, all outcome

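### The secondary mixed models leave out the two randomisation strata that the primary model includes; adding them is a nearly free gain for between-person comparisons, though not for the group×time test

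*Protocol*

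**What the plan says.** The Randomization section states: "Participants will be randomly assigned in a 1:1 ratio, stratified by sex and prior suicide attempt". Allocation uses a "permuted-block randomization sequence with variable block sizes (blocks of 4 and 6"), so there are four strata, each balanced by blocks.

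Under Statistical analysis plan, Primary analysis, the Cox model is described as "adjusting for stratification factors (sex, prior suicide attempt"). The same bullet explains the short covariate list by the number of events per variable and concludes that "the pre-specified primary model will include only the two stratification factors (sex and prior suicide attempt) as covariates".

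The next bullet, Secondary analyses, specifies "Linear mixed-effects models (random intercepts) for fixed effects: time, group, group×time; GEE/logistic models for binary outcomes (e.g., any NSSI"). The mixed models for continuous outcomes thus have a written list of fixed effects; the GEE or logistic models for binary outcomes are given no covariates. The Multiplicity bullet makes the primary outcome the only confirmatory endpoint and calls the secondary results exploratory. Hypothesis 4 expects prior attempts and sex, among other baseline factors, to be associated with outcome.

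**The concern.** Blocking within strata forces the arms to be nearly equal in sex and prior attempt. Differences between strata therefore contribute almost nothing to the true sampling variance of the arm comparison. A model without the strata does not know this: it leaves the between-stratum variation in its error term and reports a standard error larger than the real one. The test then rejects less often than 5% under the null, and some power is lost.

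The only reason the protocol gives for limiting covariates is the small number of Cox events. That does not apply to continuous scales in 150 people, and even the Cox model keeps both strata. At stake is some sensitivity on the secondary outcomes, including ideation and NSSI, where hypothesis 2 predicts an advantage for BCBT.

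**Working it through.** **Inputs from the protocol.** 75 per arm; two-sided α = 0.05; blocks of 4 and 6 in four strata; baseline plus four later main visits; d ≈ 0.38 with at least 80% power claimed for continuous secondary outcomes; 25% attrition.

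**Assumptions, because the protocol gives no value.** Within-person correlation 0.5. Strata explaining a share R² of the single-visit variance, varied from 0 to 20%. In the simulations, 60% have a prior attempt and the sexes split 70/30.

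**1. The plan's own power figure.** With SD 1, a single-visit difference has SE = √(2/75) = 0.1633. Power at d = 0.38 is Φ(0.38/0.1633 − 1.96) = 64%. Averaging four follow-up visits gives the variance factor (1 + 3 × 0.5)/4 = 0.625, so SE = √(2 × 0.625/75) = 0.1291 and power is 84%. The claim is therefore attainable for an averaged contrast, but the protocol states neither the contrast nor the correlation, so it can be neither confirmed nor refuted.

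**2. Between-person contrasts, by formula.** Let v be the variance factor (1 for one visit, 0.625 for the average) and k = √(1 − R²/v). The unadjusted model reports SE; the true SD is about k × SE.

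- Unadjusted type I error = 2 × [1 − Φ(1.96/k)]
- Unadjusted power = Φ[(0.38/SE − 1.96)/k]
- Adjusted power = Φ[0.38/(k × SE) − 1.96]

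| Contrast | R² | k | Type I error, unadjusted | Power, unadjusted | Power, adjusted |
|---|---|---|---|---|---|
| One visit | 2% | 0.990 | 4.8% | 64.5% | 65.2% |
| One visit | 10% | 0.949 | 3.9% | 65.1% | 68.9% |
| Average of four | 2% | 0.984 | 4.6% | 84.1% | 84.9% |
| Average of four | 5% | 0.959 | 4.1% | 84.7% | 86.6% |
| Average of four | 10% | 0.917 | 3.2% | 85.8% | 89.5% |

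**3. The same contrasts, by simulation.** For the follow-up average, 4,000 runs per scenario with complete data (Monte Carlo error about 0.3 points on type I error):

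| R² | Type I error, unadjusted vs adjusted | Power at d = 0.38, unadjusted vs adjusted |
|---|---|---|
| 2% | 4.5% vs 4.8% | 83% vs 84% |
| 5% | 4.0% vs 4.9% | 84% vs 86% |
| 10% | 3.4% vs 4.8% | 84% vs 89% |
| 20% | 1.7% vs 4.6% | 88% vs 95% |

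A second, separate simulation gave 3.8% at R² 5% and 3.1% at 10%, both against 4.8% adjusted, with the same power figures.

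**4. The group×time term.** This is a within-person contrast. A strata effect that is constant over time enters every visit equally and cancels. Fitted random-intercept models (60 per scenario) gave these standard errors without and with the two strata main effects:

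- complete data: 0.1629 and 0.1629, with identical estimates;
- 25% dropout, R² 5%: 0.1790 and 0.1789;
- 25% dropout, R² 20%: 0.1802 and 0.1796.

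The type I error of the change contrast stayed between 4.7% and 5.6%, with no tendency to fall as R² rose.

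**5. Binary outcome, if analysed without strata.** Single logistic model, N = 150, 2,000 runs (Monte Carlo error about 0.5 points):

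| Odds ratio of each stratum factor | Type I error, unadjusted vs adjusted | Power at treatment OR 0.40, unadjusted vs adjusted |
|---|---|---|
| 2 | 4.4% vs 4.9% | 67% vs 70% |
| 4 | 3.2% vs 5.1% | 60% vs 66% |

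The mechanism differs here. At strata OR 4 under the null, the unadjusted SE (0.336) exceeds its own sampling SD (0.309) but is smaller than the adjusted SE (0.371). Power is lost because the unadjusted estimate is attenuated: at treatment OR 0.40 its mean is −0.792, against −0.950 adjusted.

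**The case against.** The strongest counter-argument is that the secondary objective is to compare trajectories. The group×time term answers that, and step 4 shows it is not affected. This stands. A reader might infer from the omitted strata that every secondary test is conservative and underpowered; the stated model does not support that. Only strata effects that change over time could matter for group×time, and there the gain is small. In a simulation where they explained 20% of the variance of change, adjustment moved type I error from 4.0% to 4.6% and power from 85% to 87%.

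Second, the GEE/logistic clause lists no covariates at all. That is silence, which a separate statistical analysis plan may fill, and not a stated exclusion. This also stands. Only the mixed models have a written list of fixed effects that leaves the strata out.

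Third, the size depends on a prognostic strength that the protocol does not give. Hypothesis 4 predicts an association but no magnitude, and at R² of 2% the loss is about one point of power. This limits the size of the point, not its direction.

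Fourth, the outcomes are exploratory and the error cannot create false positives. This is correct, and it sets the weight of the point.

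A reader might also argue that leaving out prior attempt weakens the missing-at-random assumption. That would need dropout to depend on prior attempt beyond what the observed scores carry. The protocol says nothing on this, so it is not relied on here.

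**Conclusion.** The point holds in a limited form. The secondary mixed models omit two design factors that the primary model includes, and the protocol gives no reason. For between-person contrasts on continuous outcomes, with strata explaining 2 to 10% of single-visit variance and a within-person correlation of 0.5, type I error falls to about 4.8% to 3.1%, and about 1 to 5 points of power are lost at d = 0.38. If the strata are not prognostic, nothing is lost. Binary outcomes would be affected in the same direction, but only if the unlisted covariates turn out not to include the strata. The group×time test is essentially unaffected. The error is conservative and confined to exploratory outcomes, so this is a minor point and a free improvement; it does not threaten the trial's conclusions.

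**What to change.** In the Secondary analyses bullet, add sex and prior suicide attempt, with the values used at randomisation, as fixed effects in the linear mixed models and as covariates in the GEE/logistic models, in line with the primary Cox model.

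Stratum×time terms are optional. They go beyond the Cox model, and their cost depends on how time is coded. Table 2 schedules the BSI, BDI-II and GAD-7 at 16 time points (T0 to T15). With time as categories, the two main effects and their interactions would add 2 + 2 × 15 = 32 parameters; with linear time, 2 + 2 = 4.

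The cost is one sentence and two degrees of freedom per model. Both factors are already collected for allocation. In the logistic models the treatment odds ratio becomes conditional on the strata, and the report should say so. The change is best made before outcome data are seen.

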Brief Cognitive-Behavioral Therapy for Suicide Prevention in a Brazilian Outpatient Sample (BCBT-BR): Protocol for a Two-Arm Randomized Controlled Trial

Short title: BCBT-BR Trial Protocol

Date: May 4th, 2026

Abstract

Importance: Suicide remains a leading cause of premature mortality worldwide. While global rates have declined since 2000, the Region of the Americas shows concerning increases, particularly in Brazil. Brief Cognitive-Behavioral Therapy (BCBT) has demonstrated efficacy in reducing suicide attempts in high-income countries, but evidence from low- and middle-income countries (LMICs) and civilian outpatient settings remains limited.

Objective: To evaluate whether BCBT reduces suicide attempt incidence over 6 months compared with manualized Supportive Psychotherapy (ST) among high-risk Brazilian adults receiving university outpatient care.

Design, Setting, and Participants: Single-site, parallel-group, superiority randomized clinical trial (RCT) at the Institute of Psychiatry, University of São Paulo, Brazil. Adults aged 18-65 years with current suicidal ideation and/or suicide attempt within the past month will be randomized 1:1 to receive 12 weekly 60-minute sessions of BCBT or dose-matched ST (N=150; 75/group).

Interventions: BCBT targeting emotion regulation and cognitive reappraisal versus manualized ST providing emotional support without systematic skills training.

Main Outcomes and Measures: Primary outcome is time-to-first suicide attempt over 6 months, assessed by blinded evaluators. Secondary outcomes include suicidal ideation, non-suicidal self-injury, depression, anxiety, treatment feasibility and acceptability. Assessments occur at baseline, mid-treatment (week 6), end-of-treatment (week 12), and 3- and 6-month follow-ups, with weekly attempt surveillance. Intention-to-treat analyses will employ Cox proportional hazards regression (primary outcome) and mixed-effects/generalized linear models (secondary outcomes). Sample size provides 80% power to detect HR=0.50 ($\alpha=0.05$, 25% attrition).

Conclusions and Relevance: This trial will provide critical evidence on BCBT effectiveness in LMIC outpatient settings, informing scalable suicide prevention strategies.

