
Supplementary Material

Table 1: The structure and components of BCBT (Bryan & Rudd, 2018)

Phase	1	2	3
Sessions	1-5	6-10	11-12
Therapeutic component	Emotional Regulation and Crisis Management	Targeting Belief Systems Related to Suicide	Relapse Prevention
Techniques	Crisis Response Plan; Means restriction counseling; Sleep stimulus control; Relaxation skills training; Mindfulness skills training; Reasons for living list; Survival kitk.	ABC Worksheet ; Challenging Questions Worksheet; Problematic Patterns of Thinking Worksheet; Activity planning; Coping cards.	Relapse prevention task.

Table 2: Assessment schedule

Schedule of Assessments (CONSORT format)

Measure	T0	T1	T2	T3	T4	T5	T6	T7	T8	T9	T10	T11	T12	T13	T14	T15
Sociodemographic	X															
Treatment History	X															
Weekly Follow-up		X	X	X	X	X	X	X	X	X	X	X	X	X	X	X
BSI	X	X	X	X	X	X	X	X	X	X	X	X	X	X	X	X
BDI-II	X	X	X	X	X	X	X	X	X	X	X	X	X	X	X	X
DUREL	X	X	X	X	X	X	X	X	X	X	X	X	X	X	X	X
GAD-7	X	X	X	X	X	X	X	X	X	X	X	X	X	X	X	X
PHQ-9	X	X	X	X	X	X	X	X	X	X	X	X	X	X	X	X
PIL	X	X	X	X	X	X	X	X	X	X	X	X	X	X	X	X
SHS	X	X	X	X	X	X	X	X	X	X	X	X	X	X	X	X
SF-12	X	X	X	X	X	X	X	X	X	X	X	X	X	X	X	X
HCL-32	X	X	X	X	X	X	X	X	X	X	X	X	X	X	X	X
PROMIS Sleep	X	X	X	X	X	X	X	X	X	X	X	X	X	X	X	X
MADRS		X	X	X	X	X	X	X	X	X	X	X	X	X	X	X
C-SSRS		X	X	X	X	X	X	X	X	X	X	X	X	X	X	X
NIH BFI		X	X	X	X	X	X	X	X	X	X	X	X	X	X	X
FSS		X	X	X	X	X	X	X	X	X	X	X	X	X	X	X
SCS-R	X	X	X	X	X	X	X	X	X	X	X	X	X	X	X	X
SAFER	X	X	X	X	X	X	X	X	X	X	X	X	X	X	X	X
SAFER Follow-Up														X	X	X

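### The random-intercept model for the continuous secondary outcomes can understate the error of the linear group×time test and of late-visit contrasts, because it assumes equal correlation between all visits

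*Protocol*

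**What the plan says.** The Secondary analyses item of the protocol's Statistical analysis plan gives the model for continuous outcomes as "Linear mixed-effects models (random intercepts) for fixed effects: time, group, group×time". GEE is mentioned there only for binary outcomes. The text does not say whether time is linear or categorical. It names no random slope, within-patient correlation structure or robust standard error, and no fixed effects beyond the three listed.

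The aim this model serves is given under Objectives: "Compare trajectories of suicidal ideation, NSSI, depression, and anxiety". The group×time term therefore carries the comparison.

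Two schedules are given. The Abstract says "Assessments occur at baseline, mid-treatment (week 6), end-of-treatment (week 12), and 3- and 6-month follow-ups", which is five visits. Table 2 in the Supplementary Material has 16 columns, T0 to T15, with BSI, BDI-II and GAD-7 marked in all of them and no calendar times.

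Under Randomization, allocation is stratified by sex and prior suicide attempt. The primary Cox model adjusts for both. The Multiplicity item ranks ideation first, depression third and anxiety fourth among the secondary outcomes, plans no alpha adjustment and calls the results exploratory.

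**The concern.** A random intercept with independent residuals has two consequences. All patients in an arm share one underlying rate of change, and any two visits have the same correlation however far apart they are. In six months of treatment and follow-up in a high-risk sample, neither is likely to hold exactly.

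When patients do differ in slope, the model averages the extra within-patient variance over all visits, although it is concentrated at the ends of follow-up. The reported standard error is then too small for a linear slope contrast and for the last visit against baseline, and too large for early contrasts. The more occasions there are, the stronger the effect on the slope test.

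At stake are the confidence intervals and p-values for ideation, depression and anxiety, the outcomes on which the protocol plans to describe how the arms differ over time.

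**Working it through.** **The plan's own figure.** Under Sample size and power the protocol claims at least 80% power for a "standardized mean difference $d \approx 0.38$) on continuous secondary outcomes with repeated measures". A single-visit comparison with 75 per arm gives Φ(0.38·√(75/2) − 1.96) = Φ(0.367) = 64%. To reach 80% one has to assume a repeated-measures gain. For example, the mean of 5 visits with equal correlation 0.6 has relative variance (1 + 4·0.6)/5 = 0.68 and gives 80.6%. The same assumption with 56 per arm (75 × 0.75, for 25% attrition) gives 68%. The figure can be matched but not verified, and it yields no correlation that could be used below.

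**Inputs.** From the protocol: the model form, two-sided 5%, and 5 or 16 occasions. Assumed: intercept SD 1; residual SD σ = 0.6; individual slopes that add SD s = 0.25, 0.5 or 0.75 to change over follow-up; visits at weeks 0, 6, 12, 25, 38 (five) or weeks 0–12, 13, 26, 38 (sixteen). With s = 0.5 to 0.75 the first-to-last correlation is 0.68 to 0.62.

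**Formulas.** Scale time so that the last visit is 1, let k be the number of visits and S = Σ(t − t̄)².
- Within-patient variance that the random-intercept model pools: w = σ² + s²S/(k − 1).
- Slope contrast: (true SE / model SE)² = (σ² + s²S)/w.
- Visit t versus baseline: (true SE / model SE)² = (2σ² + s²t²)/(2w).
- True size = 2[1 − Φ(1.96/R)], where R is the SE ratio. The model SE is too small by 1 − 1/R.

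**Example, s = 0.5.** Five visits: S = 0.649, w = 0.36 + 0.25·0.649/4 = 0.4005, R² = 0.522/0.4005 = 1.304, R = 1.142, size 8.6%. Sixteen visits: S = 0.9955, w = 0.3766, R² = 0.609/0.3766 = 1.617, R = 1.272, size 12.3%.

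| Test (nominal 5%) | Visits | s = 0 | s = 0.25 | s = 0.5 | s = 0.75 |
|---|---|---|---|---|---|
| Linear group×time | 5 | 5.0% | 6.0% | 8.6% | 12.2% |
| Linear group×time | 16 | 5.0% | 6.9% | 12.3% | 19.8% |
| Last visit vs baseline | 5 | 5.0% | 5.7% | 7.5% | 10.0% |
| Last visit vs baseline | 16 | 5.0% | 5.9% | 8.4% | 12.3% |
| Week 12 vs baseline | 5 | 5.0% | 4.8% | 4.2% | 3.5% |
| Week 12 vs baseline | 16 | 5.0% | 5.0% | 4.9% | 4.7% |
| Categorical omnibus (chi-square mixture) | 5 | 5.0% | 5.0% | 5.1% | 5.6% |
| Categorical omnibus (chi-square mixture) | 16 | 5.0% | 5.1% | 5.2% | 5.8% |

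For the slope test, R runs from 1.04 to 1.27 with 5 visits and from 1.08 to 1.52 with 16. The reported SE is thus too small by 4–21% and 7–34%.

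**Visit weeks.** Ending at week 26 changes little. Five visits at weeks 0, 6, 12, 13, 26 give 5.8–11.4% for the slope test. Sixteen at weeks 0–12, 16, 20, 26 give 7.1–21.2%, with week 12 versus baseline at 5.1–5.5%.

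**Other covariance patterns.** With correlation that decays purely serially (0.90 to 0.98 per week, visits ending at week 26), the slope test has size 13–20% with 5 visits and 38–47% with 16. The omnibus test reaches 7.7% and 15%, and the first post-baseline contrast becomes strongly conservative (below 2%).

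**Simulation.** REML random-intercept fits with 25% dropout and 5 visits gave 4.7% under equal correlation (169 usable fits). Under a mixture of intercept, serial and noise variance they gave 10.4% (250 usable fits), where the formula gives 9.8%. Only these two scenarios were run with dropout.

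**The case against.** A reader might infer that all group×time tests here are anti-conservative and that the secondary results will be wrong in the liberal direction. The documents do not support that. The inflation depends on a covariance they do not give: it is nil under equal correlation and about 1 to 2 percentage points at slope SD 0.25. The text leaves the coding of time open. Under categorical time with the slope assumptions above, the omnibus test is near nominal and contrasts up to week 12 are near nominal or conservative. This part of the objection stands, and it limits the point to linear slope tests and late-visit contrasts.

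A reader might also infer that the protocol rules out any further covariance structure. It does not say that random intercepts are the only element, and a separate statistical analysis plan could add one. Still, the protocol has its own section with that title, it names the random-effects structure there, and nothing elsewhere loosens it.

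Nor do the omitted stratification factors and the unconstrained baseline cause liberal error. They mainly cost precision, and time-constant main effects drop out of group×time in balanced data.

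Finally, the secondary outcomes are exploratory, and for depression and anxiety the hypotheses predict similar improvement in both arms, so false differences there would not favour the sponsor's expectation. This lowers the stakes. Exploratory status waives multiplicity control, but it does not make a wrong standard error acceptable.

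**Conclusion.** The point holds in a conditional form. The specified model can give standard errors that are too small for the linear group×time test and for late-visit contrasts. Under the assumed SDs, a nominal 95% interval for the slope difference covers about 88–94% of the time with 5 visits and 80–93% with 16 (one minus the sizes above). The last-visit contrast has true size of about 6–12%. The direction follows from the model whenever slopes vary or correlation decays. The amount is an assumption, since neither SDs, correlations nor the calendar times of Table 2 are given. The primary Cox analysis is unaffected. The change is worth making before analysis, but it does not threaten the trial's confirmatory conclusion.

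**What to change.** State which occasions enter the model, then choose the covariance to match.

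- **Five planned visits:** time as categorical, unstructured within-patient covariance, and a named structured fallback if the fit does not converge.
- **All Table 2 occasions:** random slopes or a serial correlation structure, with robust standard errors. An unstructured matrix for 16 occasions has 16·17/2 = 136 parameters, too many for 150 patients.
- **Separately, for precision and consistency with the design:** add sex and prior suicide attempt as fixed effects, and use the baseline score as a covariate or constrain it equal between arms.

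The cost is a few sentences of text, a few more covariance parameters (5·6/2 = 15 for five visits) and the possibility of falling back to a simpler structure. No new data are needed.
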